## **Methodology**

### **Research design**

This is a stratified (female, male) with balanced randomisation (1:1), single-blind (blind endoscopist, researcher enrolling and assessing participants), placebo-controlled, parallel-group study

### **Study area**

This study will be conducted in endoscopy room in Hospital University Sains Malaysia in Kubang Kerian

### **Operative definition**

-

### **Study population**

Reference population:

- patient who has planned for OGDS

Source population

- Patient planned for OGDS and attend endoscopy room in HUSM

Study population

- Patient planned for OGDS, attend endoscopy room for in HUSM, fulfilled inclusion criteria and exclusion criteria from April 2019 until December 2019

### **Subject criteria**

Inclusion criteria

- Patient more than 18 years old

Exclusion criteria

- History of upper gastrointestinal surgery
- Intestinal obstruction
- Patient with vomiting
- Mentally disable or who cannot give an informed consent

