## **Product detail**

### **Resource**

### **Description**

Fruit flavoured beverage designed for dietary management in malnutrition and peri-operative to enhance outcomes and recovery. It is lactose and gluten free

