### **Feature**

100% high quality whey protein

Fat free

Clear fluid

Low residue

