### **Sampling method and subject recruitment**

Patient scheduled for elective OGDS in HUSM from April 2019 to December 2019 with the complaint of one or more of the following symptoms: Botherome postprandial fullness, early satiation, Epigastric pain or Epigastric burning are eligible to participate in the study. Patients who fulfilled exclusion criteria (History of upper gastrointestinal surgery, intestinal obstruction, patient with vomiting or mentally disable or who cannot give an informed consent) are ineligible.

If a patient fulfils the inclusion criteria, a suitable medical officer will discuss the trial with patient while reviewing patient in surgical outpatient clinic prior to OGDS. Patient will be approached again on the day of OGDS, if patient agree to participate in study, a written consent will be obtained. If patient refuse to participate in study, appropriate treatment and care still will be provided to patient. The consent form will provide information about the purpose of the study, the procedures to be followed,

risks and benefits of participation. If patient agree to participate in the trial, subject will be enrolled in the study. Method of recruitment in this study is direct recruitment of potential study participants.

Stratified permuted block randomization was used. Randomization sequence was created using <https://www.sealedenvelope.com/simple-randomiser/v1/lists> and is stratified by gender (female and male) with 1:1 allocation. Random block sizes of 6 is used. Subjects are randomized into either preprocedure plain water (group A) or preprocedure carbohydrate loading group (group B). Patients randomized into group A consume 250ml plain water and patients in group B consume 1 packet of resource (237ml, 53.6g carbohydrate and 9g whey protein). Both groups of patients consume the drink over 10 minutes. 2 hours after that, OGDS will be carried out.

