### **Data collection method**

All subjected planned for OGDS with the complain of one or more of the following symptoms: Bothersome postprandial fullness, early satiation, Epigastric pain or Epigastric burning and fullfill inclusion criteria are selected. Patients will be approached and be explained regarding the study in

surgical outpatient clinic prior to OGDS. Patient will be approached again on the day of OGDS, if agree to participate, an informed consent will be obtained. Informed consent will be obtained after explanation regarding the study and procedure again by researcher nurse

Allocation sequence is according computer generated random number list, it was prepared by an investigator with no clinical involvement in the trial. Allocation sequence was concealed from researcher enrolling and assessing participants. Allocation sequence will be sealed in sequentially numbered and opaque envelopes. A manila card will be placed inside envelop to render it impermeable to intense light. To prevent subversion of the allocation sequence, the name and I/C of the participant will be written on a book together with the series number on envelopes. The details in the book will be kept confidentially. After enrolled subject complete all baseline assessment, corresponding envelope will be enclosed by staff (who not involve in study) who prepare the drink. The staff need to ensure that the envelop still sealed when receive it. The staff will prepare the drink into identical container according to the assignment.

Subjects are randomised into 2 group: 1 group with 250cc plain water and another group give 1 packet resource(237ml). Subjects need to finish the drink over 10minutes. After that, subjects are not allow to leave endoscope room before OGDS done to prevent consumption of other drink or food.

2 hours after that, subject undergo OGDS. OGDS is done follow standard protocol.

1. Patient lies in left lateral position
2. Medication to numb the back of throats (spray) will be given to prevent gagging during the passage of the instrument
3. A plastic mouth guard is placed between the teeth to prevent damage to the teeth and endoscope.
4. The endoscope (also called a gastroscope) will be inserted through the mouthpiece

[figure not shown]
5. A small container or yankauer suction is placed close to the mouth of a patient to collect saliva during and after the esophagogastroduodenoscopy
6. Endoscope will be inserted along the middle line of the soft palate.

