7. Once endoscope advanced, patient may be asked to swallow to facilitate advancement of scope.
8. Throughout the procedure, no water flushing is allowed, only air inflation is allowed
9. visualised pooling of fluid in the stomach is aspirated until dry via direct visualization with endoscope. Aspirated fluid will be collected in suction reservoir and the fluid will be measured.

Subject's wellbeing is assessed via visual analogue scale (VAS) which consist of 5 parameters: hunger, thirst, anxiety, tiredness and weakness. This scale will be used repeatedly during this study to assess patient's wellbeing. Trained staff nurse will ask patient regarding level of 5 parameters and subject need to mark X somewhere along the horizontal line given before drink and before OGDS procedure.

All subjects are advised to inform assessor if there is adverse reaction. Medical personnel are available to manage any adverse events that might occur throughout the procedure.

The possible risk that may arise in the study include injury to the gastrointestinal's wall, aspiration and bleeding which is the similar risk for all patient going through OGDS procedure. Small volume of the drink will not cause psychological distress to subject, but its taste may not be palatable.

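### The exclusion criteria do not exclude patients with known whey or milk-protein allergy, although the carbohydrate arm drinks 9 g of whey protein

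*Protocol*

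**What the plan says.** **Eligibility.** Under Subject criteria, the only inclusion criterion is "Patient more than 18 years old". Sampling method and subject recruitment, and Data collection method, add an elective OGDS and at least one dyspeptic symptom. Subject criteria gives four exclusions: previous upper gastrointestinal surgery, intestinal obstruction, vomiting, and "Mentally disable or who cannot give an informed consent". Sampling method and subject recruitment repeats the same four and adds none.

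**The drink.** Sampling method and subject recruitment states that "patients in group B consume 1 packet of resource (237ml, 53.6g carbohydrate and 9g whey protein"). The product detail gives the protein source as "100% high quality whey protein". The only statement there about substances that a patient might not tolerate is "It is lactose and gluten free".

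**Safeguards.** In Data collection method, the procedural risks named are those of any OGDS. On the drink itself the text says only: "Small volume of the drink will not cause psychological distress to subject, but its taste may not be palatable". Participants are told to report an adverse reaction, and medical personnel are on hand. The pro forma records identification, allocation, age, gender, weight, height, BMI, the times of drink and scope, residual volume and the VAS scores. It does not ask about allergy.

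**The concern.** Both exclusion lists look complete, and the protocol applies them as the operative rule for who may be randomised. Whey is a milk protein. A lactose-free label concerns a milk sugar and a gluten-free label a cereal protein, so neither tells staff anything about milk-protein allergy, and a busy reader could be wrongly reassured. A patient whose allergy is already known therefore passes every written criterion. No step described between consent and drinking would bring the allergy to light. At stake is a foreseeable allergic reaction that one question before randomisation would prevent in patients who know of their allergy.

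**Working it through.** **1. Does the drink contain the stated amount of whey?** The Nutritional information table gives 3.8 g protein per 100 ml, and the pack is 237 ml. 3.8 × 2.37 = 9.006 g, which reproduces the stated 9 g. The Feature entry says that all of this protein is whey.

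**2. Would any written criterion stop an allergic patient?** Take an adult over 18 with epigastric pain, booked for elective OGDS, who has a known milk-protein allergy.

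| Criterion | Does it stop this patient? |
|---|---|
| Age over 18 | No |
| Elective OGDS with a dyspeptic symptom | No |
| Upper gastrointestinal surgery | No |
| Intestinal obstruction | No |
| Vomiting | No |
| Mental disability or inability to consent | No |

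The patient is eligible and, with 1:1 allocation, has a probability of 1/2 of receiving the whey drink.

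**3. Is there a check elsewhere?** The text shown contains no mention of allergy, hypersensitivity or milk protein. The pro forma has no such field. Reporting a reaction and having medical staff present both take effect after exposure.

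**4. How often might it happen?** The documents give no prevalence, so this is illustrative. Sample size estimation gives 35 per group, and 35 / (1 − 0.10) = 38.9, rounded up to 39 as stated. For an assumed prevalence q, the chance of at least one allergic patient among 39 in group B is 1 − (1 − q)^39, and the expected number is 39q.

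| Assumed q | Expected number in group B | Chance of at least one |
|---|---|---|
| 0.1% | 0.04 | 3.8% |
| 0.5% | 0.20 | 17.8% |
| 1% | 0.39 | 32.4% |

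These are upper figures for each q. They assume that no patient mentions the allergy or declines, and they count exposures, not reactions.

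**5. Effect on the primary comparison.** The dropout allowance is 39 − 35 = 4 per group. The expected number exposed is well below one for every q shown, so any loss of end points falls inside that allowance.

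**The case against.** The protocol states nothing false here and does not contradict itself; the point is an omission. Participants hear about the study twice, in clinic and on the day, so a patient who knows of an allergy has two chances to say so. They stay in the endoscopy room until the procedure, with medical personnel available. The consent pages and the flow figure are not shown, and either could carry a warning. All of this stands and lowers the probability and the likely severity of harm. It does not change the criteria, under which a patient who does disclose the allergy is still eligible. Eligibility belongs in the protocol and is not usually left to a SAP.

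A reader might also infer more than the text supports:

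- **That masking hides the allergen from the patient.** The protocol says "The staff will prepare the drink into identical container according to the assignment", but it does not say that the container is unmarked or that participants are blind. Research design names the endoscopist and the researcher who enrols and assesses. A fruit-flavoured drink is in any case easily told from plain water.
- **That reactions would leave one-sided missing data.** The expected numbers are too small to matter.
- **That a reaction would force unblinding.** The protocol gives no unblinding rule from which this follows.
- **That the consent form fails to warn.** Those pages were removed before review, so nothing can be said about them.
- **That no exclusion bears on the drink.** The Introduction links upper gastrointestinal surgery and obstruction to delayed emptying and aspiration, so those two are relevant to an oral load. What is missing is any criterion on its ingredients.

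**Conclusion.** The point holds as a gap in the eligibility criteria. Both exclusion lists omit known allergy to an ingredient of the study drink, one arm receives 9 g of whey protein, and nothing in the text shown identifies an allergic patient before the drink is given. The ground is participant safety alone; neither the analysis nor the sample size needs to change. The probability is low and cannot be fixed from the documents: about 4% to 18% for at least one exposure in group B under an assumed prevalence of 0.1% to 0.5%, as an upper figure. The conclusion does not rest on that range. It rests on the wording of the two lists and on whey being a milk protein. Since the possible harm is serious and the remedy is one line, the change should be made.

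**What to change.** Add to the exclusions in Subject criteria, and to their repetition in Sampling method and subject recruitment: known allergy to whey or milk protein, or to any other ingredient of the study drink. Apply it to every candidate before randomisation, so that it acts equally on both arms and leaves the comparison intact. Add a matching yes/no item to the pro forma, completed before the allocation envelope is opened. In the risk text of Data collection method, add allergic reaction to the drink.

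The cost is one criterion in two places, one form item and one sentence. The loss of recruitment is negligible, and the target of 39 per group stays as it is. The check catches only allergies that the patient already knows of, so the existing arrangements for reporting a reaction are still needed.

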### **End points**

#### Primary end point

- Amount of gastric residual volume (ml) that has been aspirated via OGDS 2 hours after plain water or carbohydrate loading group

#### Secondary end point

- Score (mm) of each parameter from visual analogue scale (VAS) before drink and before OGDS for plain water and carbohydrate loading group

### **Sample size estimation**

Sample size is calculated for all the objectives. However, the one that yield the biggest number is taken as the sample size.

objective 1 is to identify the gastric residual volume between subject with plain water (group A) and carbohydrate loading (group B). Sample size was calculated using comparing two means formula. Sample size is calculate using <http://www.openepi.com/SampleSize/SSMean.htm>. The ratio between group A and group B was set as 1. According to article, standard deviation was 18.46. Means difference was set as 12.5. sample size for objective 1 is 35 per group.

Objective 2 is to determined patient's well being for group A and group B. sample size was calculate using comparing paired difference formula. Sample size calculate using <http://statulator.com/SampleSize/ss2PM.html#>. Expected standard deviation of the paired

differences is set as 2 times the expected mean of the paired differences. The sample size is 34 per group

For all sample size calculation, type I error was set at 5% (two tailed), Type 2 error was 20% (to achieve 80% power of study).

Corrected sample size is calculated after included 10% of dropout rate. Corrected sample size = calculated sample size/ (1-anticipated drop out rate).

After considering both objective, 1st objective give biggest number of sample size. Hence, 35 subject per group with a total number of 70 subjects are needed to study both objectives. after consider dropout rate, minimum sample size in this study is 39 subjects per group with a total number of 78 subjects.

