### Second hypothesis

H1: there is significant association between carbohydrate loading with subject's wellbeing

H0: there is no significant association between carbohydrate loading with subject's wellbeing

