## **Data analysis**

The collected data will be entry and analyzed using SPSS version 24 (SPSS Inc., Chicago, IL, USA)

Objective 1 is to determine and compare gastric residual volume between group A and group B subjects. Independent T test is used to interpret the date.

Objective 2 is to determine and compare subject's well being before and after drink in between group A and group B. paired t test is used to determine effect of drink on subject's wellbeing before and after in each group. ANOVA is used to compare effect of the drink in both groups.

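### Objective 2 was sized only for the before/after test within one group, so the claim that 35 per group serves both objectives does not cover the between-group wellbeing comparison

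*Protocol*

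**What the plan says.** The Sample size estimation section opens with a general claim: "Sample size is calculated for all the objectives". The largest result is then to be used. Objective 1 (gastric residual volume) is sized by comparing two means, giving 35 per group. For objective 2, "sample size was calculate using comparing paired difference formula"; the SD of the paired differences is taken as twice their mean, and the result is 34 per group. The error rates are common to all the calculations: two-sided 5%, and "Type 2 error was 20% (to achieve 80% power of study". The section concludes that "35 subject per group with a total number of 70 subjects are needed to study both objectives", raised to 39 per group (78 in total) for 10% dropout.

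The Data analysis section describes objective 2 more broadly. It is to determine and compare the subject's "well being before and after drink in between group A and group B". Two tests are assigned to it. Within each group, a "paired t test is used to determine effect of drink on" wellbeing. Across groups, "ANOVA is used to compare effect of the drink in both groups".

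The second hypothesis reads "H1: there is significant association between carbohydrate loading with" the subject's wellbeing. The Research design section describes a 1:1 randomised, parallel-group trial.

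**The concern.** A paired-difference formula contains no between-group term. It answers whether scores in one arm move between the drink and the endoscopy. Objective 2, as the Data analysis section defines it, and the second hypothesis also ask whether the two drinks differ. That is a different contrast with a different variance, and the protocol gives it no effect size, SD or power.

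The distinction matters because a change inside one arm mixes the effect of the drink with the effect of two hours of waiting. Only the randomised comparison separates them. As the sample size section stands, a reader could take a null between-group wellbeing result to come from a comparison with 80% power, when no such figure was derived.

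**Working it through.** **Inputs from the Sample size estimation section.** Two-sided 5%, 80% power, ratio 1:1. Objective 1: SD 18.46 ml, difference 12.5 ml. Objective 2: SD of paired differences = 2 × mean difference, a standardised effect of 1/2 = 0.5. Dropout 10%.

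**1. The protocol's own figures reproduce.**
- Objective 1: n = 2 × (18.46 × 2.802 / 12.5)² = 34.2, so 35 per group.
- Objective 2, paired: (2 × 2.802)² = 31.4 by the normal approximation. Adding 1.96²/2 = 1.92 gives 33.3, so 34. With the noncentral t (noncentrality 0.5√n, n − 1 df), power is 79.5% at 33, 80.8% at 34, 82.0% at 35 and 86.1% at 39.
- Dropout: 35/0.9 = 38.9, so 39.

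None of these is disputed. The 34 is the number of subjects for one before/after test in one group.

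**2. What the between-group comparison would have at 35 per group.** The protocol gives neither a between-group difference nor the form of the ANOVA, so this step rests on assumptions: equal SDs, two-sided 5%, 35 evaluable per group, and a between-group difference in mean change of 0.5 SD of change. The 0.5 is carried over from the within-group input for illustration only.

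Let s be the SD of a single score and r the before/after correlation. Then SD of change = s√(2(1 − r)). The noncentralities for n per group are:
- change scores (group-by-time): 0.5√(n/2) = 0.5√17.5 = 2.09, whatever r is;
- baseline-adjusted, residual SD s√(1 − r²): 0.5√(n/(1 + r)), with 67 df;
- final scores only, SD s: 0.5√(n(1 − r)), with 68 df.

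| Analysis | r = 0 | r = 0.3 | r = 0.5 | r = 0.7 |
|---|---|---|---|---|
| Change scores | 54% | 54% | 54% | 54% |
| Baseline-adjusted | 83% | 73% | 66% | 61% |
| Final scores | 83% | 68% | 54% | 36% |

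A simulation of the baseline-adjusted analysis (6,000 runs) gave 72% at r = 0.3 and 60% at r = 0.7, in agreement. If all 39 per group were evaluable, the change-score figure would be 59% and the baseline-adjusted range 66% to 77% (r from 0.7 to 0.3).

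**3. Difference detectable with 80% power at 35 per group, in SD of change.**
- Change scores: 0.68.
- Baseline-adjusted: 0.55, 0.59 and 0.63 at r = 0.3, 0.5 and 0.7.
- Final scores: 0.57, 0.68 and 0.88 at the same correlations.

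On change scores, 80% power for 0.5 SD would need 64 per group by the t test (63 by the normal approximation), roughly twice the 34 obtained from the paired formula.

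**The case against.** The strongest reply is that the protocol is open about what it did. It names the paired formula, gives the SD assumption and reports 34 per group, which matches the paired t test planned in each group. The 80% can be read as attaching only to the calculations actually made, and no power is claimed for the ANOVA by name. Wellbeing is a secondary end point, and the specific objective is worded as exploring it, so not every test on it needs 80% power. The between-group power figures depend on an effect the protocol never states. Part of their spread also comes from scaling: expressed in SD of change, the assumed difference falls from 0.71 to 0.39 SD of a single score as r goes from 0 to 0.7. Finally, a reported confidence interval would show the precision whatever the planning text says.

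Much of this stands. There is no arithmetic error, the weight is that of a secondary endpoint, and the power range settles nothing about adequacy. It does not rescue the sufficiency statement. The section says that all objectives were sized and that 35 per group serve both, while the Data analysis section puts the between-group comparison inside objective 2 and the second hypothesis frames it as a formal test. A later analysis plan could specify the ANOVA, but it would not correct a claim already made in the protocol.

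**Conclusion.** The concern holds and should be fixed. The claim that 35 per group is enough for both objectives is supported for objective 1 and for the within-group part of objective 2. It has no basis for the between-group wellbeing comparison, which is the one that answers the second hypothesis. The conclusion needs no assumed effect size: it follows from the absence of any between-group effect or SD in the protocol.

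The size of the gap does depend on assumptions. At 0.5 SD of change and 35 evaluable per group, between-group power runs from 36% to 83% across the analyses and correlations tabulated. If the true difference were about 0.68 SD of change or more, 35 per group would give at least 80% even on change scores; the protocol neither states nor justifies such a value. The comparison is therefore unsupported, not shown to be underpowered. The primary endpoint sizing is not touched.

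**What to change.** Keep enrolment and the planned tests, and narrow the power statement in the Sample size estimation section. Suggested text to replace the conclusion about both objectives:

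> With 35 evaluable subjects per group the study has about 80% power for objective 1. For objective 2, 34 per group gives 80% power to detect a before/after change of 0.5 SD of the paired differences within one group (paired t test). The between-group wellbeing comparison was not separately powered.

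The opening claim that all objectives were sized needs the same limit. The power figures should be stated on one basis: at 35 per group objective 1 has 80% by the normal approximation and 79.7% by the exact t test, while the 80.8% for the paired test at 34 is exact.

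If a sensitivity figure is wanted, give it with its assumptions. On change scores, with equal SDs and two-sided 5%, 35 evaluable per group has 80% power for a difference in mean change of about 0.68 SD of change, and about 54% for 0.5 SD. At 0.5 SD a baseline-adjusted analysis has about 61% to 73% for an assumed before/after correlation of 0.7 to 0.3.

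The cost is wording only: no extra patients and no change to the tests. The stated power for a secondary endpoint becomes less favourable.
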